6.1.6. Pooling of Sites

Analysis sites (pooled sites) will be created if any site has fewer than 6 randomized subjects. Site 004 will be one analysis site and all other sites will be combined into a second analysis site. The final determination of pooled sites will be made prior to database lock. Should the condition for multiple imputation be met, analysis site will be used in the multiple imputation model.

6.1.7. Derived Variables

6.1.7.1. General

- **Age:** Age will be calculated as the integer difference in years between the subject's date of informed consent and the date of birth.

- **Baseline:** The last observation prior to the first dose of study drug. See Section 6.1.1 for more detail.
- **Change from baseline:** The value at the target time point minus the value at baseline.
- **Prior and concomitant medications:** All medications taken in the month prior to Visit 1 (Screening) or in the time interval between Visit 1 (Screening) and Visit 2 (Baseline) will be considered prior medications, whether or not they were stopped before Visit 2 (Baseline). Any medications continuing or starting after Visit 2 (Baseline) will be considered concomitant. If a medication starts before Visit 2 (Baseline) and continues after Visit 2 (Baseline) it will be considered both prior and concomitant.
- **Study day:** For analysis purposes, Study day is calculated relative to the date of first dose of study drug.
- **Treatment emergent adverse event (TEAE):** Treatment emergent adverse events are defined as 1) AEs with onset at the time of or following the start of treatment with IP through Visit 7 (Follow-Up) or 2) AEs starting prior to the start of treatment but increasing in severity or relationship at the time of, or following, the start of treatment with IP through Visit 7 (Follow-Up).
- **Total vial weight dispensed (grams):** Subjects will be dispensed 2 vials of the appropriate IP at Visits 2, 3, 4, and 5. The vial weights will be recorded prior to dispensation. For each subject and visit where vials were dispensed, calculate the total vial weight dispensed as the sum of the weight of the 2 vials prior to dispensation. If a subject is missing a weight for one or both vials at a visit, then the total vial weight dispensed at that visit will be set to missing.
- **Total vial weight returned (grams):** At Visits 3, 4, 5, and 6, subjects will return the IP vials that were dispensed at the previous visit. The weights of the returned vials will be recorded. For each subject and visit where vials were returned, calculate the total vial weight returned as the sum of the weight of the 2 vials returned. If a subject is missing a weight for one or both vials at a visit, then the total vial weight returned at that visit will be set to missing.
- **Difference in vial weight (grams):** For each subject, for Visits 3, 4, 5, and 6, the difference in vial weight will be calculated as: total vial weight returned at current visit minus total vial weight dispensed at previous visit. For example, the difference in vial weight at Visit 3 will be calculated as the difference in total vial weight returned at Visit 3 minus the total vial weight dispensed at Visit 2. If a subject is missing a value for total vial weight returned or total vial weight dispensed needed for the computation of difference in vial weight for a given visit, then the value of difference in vial weight for that visit will be set to missing.
- **Doses missing:** The number of doses missing will be computed for each subject and each visit where vials are returned (Visits 3, 4, 5, and 6). Doses missing for a given visit will be calculated as the absolute value of the difference in vial weight for the visit, divided by 0.2. If the difference in vial weight for a given subject and visit is missing, then the number of doses missing will be set to missing.

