9.2. Selection of Timing of Dose for Each Subject

Before initiation of treatment with the IP at Baseline (Visit 2), subjects will be trained by the Investigator or delegated staff in the proper technique for priming and self-administration of IP as outlined in the Study Manual.

The IP is to be delivered i.n. with the nozzle of the applicator positioned in the nasal vestibule and directed toward the midline (lower anterior part or nasal septum). To administer study medication, the actuator (pusher) should be depressed completely.

Prior to the use of a new IP vial, subjects will prime the spray pump by depressing the actuator 4 times. [REDACTED] After

the new IP vial has been primed for the first administration, only one priming spray is required for subsequent doses.

Subjects will be instructed to administer [REDACTED]

[REDACTED] The administration will be done during waking hours and the suggested spacing is at morning, noon, early evening, and bedtime.

[REDACTED] Placebo IP is one 100 µL spray per nostril for a total

of 200 µL. Study drug will be self-administered 4 times a day. The spacing between doses needs to be at least 2 hours.

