10.2.2 Baseline (Visit 2)

For subjects continuing to meet all eligibility criteria, the following assessments will be completed at Baseline (Visit 2):

- Subject to fill out ADNM
- Administer MADRS
- Administer HAM-A

- Administer C-SSRS (since last visit)
- Administer CGI-S
- Administer IADQ
- Measure vital signs after the subject has rested for 5 minutes: seated systolic and diastolic blood pressure, heart rate, respiratory rate, and body temperature
- Obtain blood and urine samples for clinical laboratory examination, including hematology, chemistry, prolactin, thyroid functioning, and urinalysis (refer to Section 10.3.2.1.1 for complete list)
- Obtain urine sample for urine drug screen: Instant Exam to be performed on site, with results thoroughly documented in the source
- For females of childbearing potential, obtain urine sample and complete on-site urine pregnancy test
- Record concomitant medication use including the completion of any washout
- Review all inclusion and exclusion criteria

For subjects meeting all study inclusion criteria and no study exclusion criteria, (after review of the assessments above) the following Visit 2 procedures will be performed:

- Randomize the subject and obtain first IP vial
- Train subjects on use of IP and dosing
- Prior to giving a vial(s) to the subject, site staff will identify/mark the vials as vial #1 and vial #2. Staff will then instruct the subject on initial priming and ongoing priming, as outlined in the Study Manual
- Both IP vials will be weighed (as per instructions in the Study Manual). The subject will then complete the initial priming and self-administer the first dose in the presence of site personnel
- Record any AEs reported after IP administration

The next visit (Visit 3) will be scheduled 1 week (± 2 days) after the date of Baseline (Visit 2).

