13.1.3 Exposure and Compliance

Investigational product administration will be summarized in terms of number of doses received (PH94B and placebo). Descriptive statistics for categorical data will be provided by treatment group.

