7.4. Exposure and Compliance

Drug and placebo will be supplied in identical 10 mL amber glass vials with metered dose spray nozzle containing 8 mL of IP. Both drug and placebo nozzles will deliver 100 µL of IP. Each vial contains 40 doses of IP (8 mL/200 µL/dose = 40 doses). Subjects will be dispensed 2 vials of IP at Visit 2 (Baseline) and Visits 3 through 5. Vial weights will be recorded prior to dispensation. At Visits 3 through 6, the 3 vials dispensed at the previous visit will be returned. Weights of the returned vials will be recorded.

The difference in vial weight and doses missing will be computed for each subject and visit for which vials were returned (Visits 3 through 6). Details of these calculations are provided in Section 6.1.7.1. The calculation for doses missing does not differentiate between doses administered for priming purposes versus doses administered to the nasal cavity. It is assumed that priming practices are uniform across subjects and treatment groups. Differences in vial weight, differences in vial volume, and doses missing will be summarized by visit, overall and by treatment group for the Safety population.

8. Efficacy Analysis

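### The SAP's 'Doses missing' is product used, priming included: an unused week reads 0 and a fully adherent week about 45

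*SAP*

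**What the plan says.** SAP 6.1.7.1 adds the weights of the two vials at dispensing and again at return, and takes returned minus dispensed. *Doses missing* then "will be calculated as the absolute value of the difference in vial weight for the visit, divided by 0.2". The footnote to the Table 14.1.6 shell (Exposure to Study Drug) repeats the formula. SAP 7.4 gives 8 mL per vial, 100 µL per spray, 200 µL per dose and hence 40 doses per vial. It also discloses: "The calculation for doses missing does not differentiate between doses administered for priming purposes versus doses administered to the nasal cavity". Priming is assumed uniform across subjects and groups.

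Protocol 9.2 says that before a new vial is used, "subjects will prime the spray pump by depressing the actuator 4 times"; after that, "only one priming spray is required for subsequent doses". Protocol 9.4 puts weighing ahead of priming and the first dose. Protocol 10.2.2 has the same order: both vials are weighed, and "The subject will then complete the initial priming and self-administer the first dose in the presence of site personnel".

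Protocol 13.1.3 states that exposure will be reported as the number of doses received. Table 14.1.6 is the only exposure table planned, and its rows are the weight difference and *Doses missing*. Listing 16.2.5.2 covers only the first dose. SAP section 11 lists other departures from the protocol but not this one.

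Two further statements in SAP 7.4 bear on the same derivation. It says that "the 3 vials dispensed at the previous visit will be returned", although 2 are dispensed and 6.1.7.1 tells the analyst to "calculate the total vial weight returned as the sum of the weight of the 2 vials returned". It also promises a summary of the difference in vial volume, which 6.1.7.1 does not define and the shell does not show.

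**The concern.** In an exposure table, a row called *Doses missing* invites the reading 'doses not taken'. The formula moves the other way: the more a subject uses, the higher the value. A reader who goes by the label would rate a subject who took half the doses as more adherent than one who took them all.

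Correcting the direction does not make the number a dose count, because each priming spray is charged as if it were dosing. At stake is whether the study report can say how much treatment subjects took, which the protocol promises and no other planned output supplies.

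**Working it through.** **Inputs.** Spray 0.1 mL, dose 2 sprays = 0.2 mL, vial 8 mL (SAP 7.4). Four doses a day, so 28 in a nominal 7-day interval; 4 priming sprays for a new vial and 1 before each later dose (Protocol 9.2). Weighing precedes priming (Protocol 9.4, 10.2.2). Product density is not given: 1 g/mL is assumed, with a range of 0.95 to 1.05.

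**The SAP's own figure.** 8 / 0.2 = 40 doses per vial. This reproduces, as capacity before priming.

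**Volume used under Protocol 9.2 priming.** For k doses from one vial: 0.4 + 0.2 + 0.3(k − 1) = 0.3k + 0.3 mL. For k = 25 this is 7.8 mL. For k = 26 it would be 8.1 mL, more than the vial holds. One vial therefore yields 25 doses, and 28 doses need 25 from the first vial and 3 from the second: 7.8 + 1.2 = 9.0 mL.

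**SAP reading** = volume × density / 0.2. At 1 g/mL:

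| Doses taken (of 28) | Volume used (mL) | *Doses missing* reads | Doses actually missed |
|---|---|---|---|
| 0 | 0 | 0 | 28 |
| 1 | 0.6 | 3 | 27 |
| 14 | 4.5 | 22.5 | 14 |
| 18 | 5.7 | 28.5 | 10 |
| 28 | 9.0 | 45 | 0 |

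The 1-dose row is a subject who takes the supervised dose at Visit 2 and then stops. The 18-dose row shows why renaming alone is not enough: a reading near 28 corresponds to 18/28 = 64% of doses if priming follows the protocol.

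**Sensitivity for 28 doses taken.**
- Density: 9.0 × 0.95 / 0.2 = 42.75; 9.0 × 1.05 / 0.2 = 47.25.
- Priming, at 1 g/mL: none, 5.6 / 0.2 = 28; initial priming of one vial only, 6.0 / 0.2 = 30; initial priming of two vials only, 6.4 / 0.2 = 32.

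**Expected volume by interval, Protocol 9.2 priming.**
- 5 days, 20 doses: 0.3 × 20 + 0.3 = 6.3 mL.
- 7 days, 28 doses: 9.0 mL.
- 9 days, 36 doses (25 + 11): 7.8 + 3.6 = 11.4 mL.

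**Can doses taken be recovered?** Inverting the volume formula gives (volume − 0.3) / 0.3 per vial. For 28 doses with protocol priming: (7.8 − 0.3)/0.3 + (1.2 − 0.3)/0.3 = 25 + 3 = 28. The result is not a bound:
- Applied to grams at 1.05 g/mL, the losses of 8.19 and 1.26 give 26.3 and 3.2. Rounded down, these total 29, more than were taken.
- For a subject who primes one vial once and never again, (6.0 − 0.3)/0.3 = 19, far fewer than the 28 taken.

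It is an estimate that holds only for a known density and protocol priming.

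**The case against.** The SAP is open about what it computes. The formula is printed under the table, and the sentence on priming speaks of doses administered, so the authors evidently meant product missing from the vial. On that reading the variable is computed as defined and the fault lies in its name. That stands: this is not a calculation error, and only a reader who passes over the footnote would rank adherence backwards.

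It also stands that the protocol's exposure measure was not simply dropped. Weight loss / 0.2 is an inflated stand-in for doses received, and the fair criticism is that the substitution is neither named nor declared.

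A third objection is that part of Protocol 9.2 is redacted around the priming text, and that Protocol 9.4 places the compliance calculation in the Study Manual, which is not available here. An expected-use comparison may exist there. This limits confidence in 45 as a figure, but not in the direction of the variable. No planned SAP output uses such a comparison.

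A reader might go further and infer that the comparison between arms is biased, that the 40 doses per vial are wrong, or that efficacy results are affected. The documents support none of these. Uniform priming cancels between arms, 40 is correct as nominal capacity, and no efficacy analysis uses the variable. SAP 7.2 names poor adherence as an example of an important deviation, but the SAP sets no compliance cut-off based on vial weight.

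**Conclusion.** The point holds as a minor one, confined to exposure reporting. *Doses missing* is product used in 0.2 g units with priming included. It reads 0 for no use and about 45 for a fully adherent 7-day week. The 45 rests on an assumed density of 1 g/mL and on the visible Protocol 9.2 priming. The upward direction, and the absence of any scheduled count, depend on neither assumption. Disclosure of the priming convention leaves the label and the absolute level uncorrected, and the departure from Protocol 13.1.3 is undeclared.

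**What to change.** 1. Rename the variable 'dose-equivalents used (including priming)' in SAP 6.1.7.1, SAP 7.4 and Table 14.1.6.
2. Convert weight loss to volume with the product's known density. Beside it show the expected volume for the actual interval under Protocol 9.2 priming (6.3, 9.0 and 11.4 mL for 5, 7 and 9 days), after checking these against the Study Manual's priming instructions and compliance calculation.
3. If a doses-taken figure is wanted, derive it per vial in mL as (volume loss − 0.3)/0.3, scoring 0 for a vial that lost less than 0.6 mL (initial priming plus one dose). Label it an estimate conditional on Protocol 9.2 priming and the stated density, not a bound.
4. Declare in SAP section 11 that these measures replace the number of doses received.
5. In SAP 7.4, reconcile the 3 vials returned with the 2 dispensed, and either define the difference in vial volume as weight loss divided by density or delete it.

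The cost is one or two extra rows per visit, a footnote and a few wording edits. No new subject data are needed, because Listing 16.2.5.1 already holds each vial's weight; the density must be obtained from the product records. The downside is that any doses-taken figure rests on stated assumptions, since weight alone cannot separate priming from dosing.

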6.1.7.2. Hamilton Anxiety (HAM-A) Scale

At each visit, subjects will be asked to complete the HAM-A questionnaire to assess anxiety. The HAM-A questionnaire consists of 14 items, each scored on a 5-point scale (0=“Not present”, 1=“Mild”, 2=“Moderate”, 3=“Severe”, 4=“Very severe”). It is completed by trained personnel over a 15-to-20-minute period. The Structured Interview Guide for the HAM-A (SIGH-A) will be used.

The Hamilton Anxiety Scale (HAM-A) total score is calculated as the sum of the 14 individual scores, ranging from 0 to 56 where <17 indicates mild severity, 18-24 mild to moderate severity, and 25-30 moderate to severe.

The fraction of missing change from baseline to Visit 6 HAM-A total scores is calculated as the number of missing values of change from baseline to Visit 6 HAM-A total scores across all subjects in the ITT population divided by the total number of expected change scores (1 per subject in the ITT population). The fraction of missing change from baseline to Visit 6 HAM-A total scores is used to compute the threshold for determining whether to implement the multiple imputation procedure, as described in Section 6.1.4.

6.1.7.3. Clinician’s Global Impression – Improvement (CGI-I) Scale

The CGI scale is a clinician-rated scale assessment of the clinician’s view of the subject’s global health prior to and after participation in a clinical study. The improvement component (CGI-I) asks the clinician to respond to the following question:

“Rate total improvement whether or not, in your judgement, it is due entirely to drug treatment. Compared to his condition at admission to the project, how much has he changed?”

The rating is on an 8-point scale (0=“Not assessed”, 1=“Very much improved”, 2=“Much improved”, 3=“Minimally Improved”, 4=“No change”, 5=“Minimally worse”, 6=“Much worse”, 7=“Very much worse”).

Subjects with scores of 1 (Very much improved) or 2 (Much improved) at the end of treatment with PH94B will be categorized as “responders”. The proportion of CGI-I responders will be calculated as the number of CGI-I responders divided by the number of subjects with non-missing CGI-I scores in the population of interest.

6.1.7.4. Patient’s Global Impression of Change (PGI-C)

The PGI-C is a self-administered instrument that measures change in subjects’ overall improvement with treatment. The subject will respond to the following question using the same scale as is used for the CGI-I (Section 6.1.7.3):

“Since the start of the study, my overall status is _____.”

Subjects reporting scores of 1 (Very much improved) or 2 (Much improved) at the end of treatment with PH94B will be categorized as “responders”. The proportion of PGI-C responders

will be calculated as the number of PGI-C responders divided by the number of subjects with non-missing PGI-C scores in the population of interest.

6.1.7.5. Adjustment Disorder New Module (ADNM) Scale

The ADNM is a newer scale that has been validated for classification of severity of adjustment disorder (AjD). It consists of an 18-item stressful life event checklist and a list of 20 statements about which reactions these types of events can trigger. Subjects are also asked to indicate how often the statements apply to them on a 4-point scale (1=“never”, 2=“rarely”, 3=“sometimes”, and 4=“often”).

The ADNM total score is calculated as the sum of the 20 statement frequency scores. The subscale scores will be calculated as the sum of the statement frequency scores indicated below.

- Preoccupation Subscore: 2, 4, 13, and 15
- Failure to Adapt Subscore: 10, 17, 19, and 20
- Avoidance Subscore: 3, 7, 11, and 14
- Depressed Mood Subscore: 1, 5, and 18
- Anxiety Subscore: 6 and 16
- Impulse Disturbance Subscore: 8, 9, and 12

6.1.7.6. International Adjustment Disorder Questionnaire (IADQ)

The IADQ is a recently validated questionnaire to measure AjD symptoms defined by the new International Classification of Disorders (ICD-11) definition. The subject completes a 9-item checklist of potential stressful events, and if they have experienced any stressful events, they then complete a 3-item list of potential problems suffered over the last month (Preoccupation subscale), a 3-item list of potential social impacts from the stressors (Failure to Adapt subscale), 1 regarding timing of symptoms, and a 3-item list of potential functional impairments (Functional Impairment). The Preoccupation, Failure to Adapt, and Functional Impairment items are scored on a 5-point scale (0=“Not at all”, 1=“A little bit”, 2=“Moderately”, 3=“Quite a bit”, and 4=“Extremely”).

The IADQ total score is calculated as the sum of the 6 Preoccupation and Failure to Adapt items (items 10 through 15). The Preoccupation and Failure to Adapt subscale scores will be calculated as the sums of the individual scores for items 10, 11, and 12 (Preoccupation) and 13, 14, and 15 (Failure to Adapt), respectively. An additional Functional Impairment subscale score will be calculated as the sum of the individual scores on items 17, 18, and 19 (not included in the total score).

6.1.7.7. Liebowitz Social Anxiety Scale (LSAS)

The LSAS is a clinician-rated scale that has been shown to be sensitive to treatment-related change in social phobia symptoms. The time frame for rating symptomatology is the past week. The scale consists of 24 items. Each item is given 2 ratings: fear or anxiety on scale of 0 to 3 and avoidance on a scale of 0 to 3, with a total maximum overall score of 144. The “Total

Performance (P) Subscore – Fear or Anxiety” and the “Total Performance Subscore (P) – Avoidance” are the sums of the fear or anxiety or avoidance scores, respectively, on items 1-4, 6, 8, 9, 13, 14, 16, 17, 20, and 21. The “Total Social (S) Subscore – Fear or Anxiety” and “Total Social (S) Subscore – Avoidance” are the sums of the fear or anxiety or avoidance scores, respectively, on items 5, 7, 10-12, 15, 18, 19, and 22-24. The “Total Anxiety Subscore” and the “Total Avoidance Subscore” are the sums of performance and social subscores for fear or anxiety and avoidance scales, respectively. The LSAS total score for each subject is the sum of all ratings across both scales.

6.1.7.8. Montgomery-Asberg Depression Rating Scale (MADRS)

The MADRS is a validated instrument used to measure the severity of depressive episodes. A higher MADRS score indicates more severe depression. The MADRS includes 10 items and uses a 0 to 6 severity scale.

The MADRS total score will be calculated as the sum of the 10 items and will range from 0 to 60.

6.1.7.9. Columbia-Suicide Severity Rating Scale (C-SSRS)

The C-SSRS is a semi-structured interview that captures the occurrence, severity, and frequency of suicide-related thoughts and behaviors during the assessment period. The interview includes definitions and suggested questions to solicit the type of information needed to determine if a suicide-related thought or behavior has occurred. The C-SSRS has a “baseline” version, which will be completed at Visit 1 (Screening), and a “since last visit” version that will be completed at all subsequent visits.

There are a maximum of 19 items to be completed: 7 that are required, 10 potential additional items if there is a positive response to a required item, and 2 items for suicide/suicide behavior present during the interview. The C-SSRS uses dichotomous scales (i.e., yes or no), Likert scales, and text or narrative are used to further describe the thoughts or behaviors.

Subjects are considered to have had suicidal ideation during a time period (lifetime, last 6 months, since last visit) if they respond “Yes” to any of the 5 suicidal ideation questions listed below for that time period:

- Wish to be dead (Category 1)
- Non-specific active suicidal thoughts (Category 2)
- Active suicidal ideation with any methods (Category 3)
- Active suicidal ideation with some intent to act, without specific plan (Category 4)
- Active suicidal ideation with specific plan and intent (Category 5)

Subjects are considered to have had suicidal behavior during a time period if they respond “Yes” to any of the 5 suicidal behavior questions listed below for that time period:

- Completed suicide
- Actual attempt

- Interrupted attempt
- Aborted attempt
- Preparatory acts or behavior

Subjects are considered to have suicidal ideation or behavior during a time period if they responded “Yes” to any of the suicidal ideation or behavior questions for that time period.

A subject’s maximum suicidal ideation score is the maximum suicidal ideation category to which they responded “Yes”. Subjects are considered to have treatment emergent suicidal ideation if their maximum suicidal ideation score increased from a previous visit to the next visit after treatment with study drug.

Subjects are considered to have treatment emergent suicidal behavior if they did not have suicidal behavior prior to treatment with study drug but did have suicidal behavior at any visit after treatment with study drug.

